4.1. Name

4.2. All geographic subdivisions smaller than a State, including street address, city, county, precinct, zip code, and their equivalent geocodes, except for the initial three digits of a zip code if, according to the current publicly available data from the Bureau of the Census

4.3. All elements of dates (except year) for dates directly related to an individual, and all ages over 89 and all elements of dates (including year) indicative of such age, except that such ages and elements may be aggregated into a single category of age 90 or older.

4.3.1. Birth Date Date of Death

4.3.2. Discharge date Admission date

4.3.3. Appointment Dates Other Dates (e.g. lab tests, x-rays, MRI, etc.)

4.4. Telephone numbers

4.5. Fax numbers

4.6. Electronic mail addresses

4.7. Social Security/Medical Record Number

4.8. Health plan beneficiary numbers

4.9. Account Numbers

4.10. Certificate/license numbers

4.11. Vehicle identifiers and serial numbers, including license plate numbers

4.12. Device identifiers and serial numbers

4.13. Web universal resource locators (URLS)

4.14. Internet protocol (IP) address numbers

4.15. Biometric identifiers, including fingerprints, voiceprints, audio recordings

4.16. Full-face photographic images and any comparable images

4.17. Any other unique identifying number, characteristic, or code

4.18. Personal and Family History

4.19. History and Physical Examination Progress Notes

4.20. Discharge Summary(ies) Photographs, videotapes, other images

4.21. X-Ray HIV (testing or infectious disease) records

4.22. Diagnostic/Laboratory tests Sickle cell anemia

4.23. Drug Abuse Information Behavioral Health notes

4.24. Alcoholism or Alcohol Use Operative Reports

4.25. Billing records Medication List

4.26. Health Summary Reports Anatomic Pathology Report

4.27. Other Records: Supported Employment records

5. **Will participants be contacted from existing PHI?** YES NO N/A

5.1. If yes, clearly explain how participants will be contacted (NOTE: this would be the same information as listed under section R.8 identification and recruitment of subjects). **Potential participants will be identified through the outpatient mental health clinic, the inpatient psychiatric unit, and the Compensated Work Therapy (CWT) program at the CMCVAMC. Identification of potential research participants will be two-fold: (1) the research team will conduct a review of the caseloads of the treating psychiatrists in the CMCVAMC outpatient mental health clinic and inpatient psychiatric unit via CPRS review under a Waiver of Individual Authorization for Disclosure of Protected Health Information. The research team will communicate securely (e.g., via CPRS, encrypted email, secure server) regarding patients who may be eligible for the research study, and confer on the appropriateness of research participation; (2) treating psychiatrists in the outpatient mental health clinic and inpatient psychiatric unit will identify potentially eligible participants based on interest in SE and interest in learning about research. In either case, treating psychiatrists at the outpatient mental health clinic and inpatient psychiatric unit will refer individuals with SMI as per CMCVAMC standard protocol to the CWT program. (This referral would be made**

regardless of eligibility in the research study.) Providers who refer potentially appropriate Veterans will ask them if they would consider participating in the research study. The study team will remind the clinician that they should document this referral in the patient's chart. Those who agree will be approached by the research staff (the PI, RC, independent assessors, and/or the SE specialists) after they are referred to the CWT program through a CPRS consult created specifically for study referrals (i.e., SE Research Consult – Vocational Rehab Outpt). The consult note will remind providers that they can only refer patients who want to hear more about the study. The study team will receive an alert in the CPRS system once a study consult has been placed. The study team will regularly check for consults in the CPRS system. All consults will be received and resolved by the study team within 24 business hours, per CMCVAMC standard of care. Providers and the research team may also collaborate to identify potentially eligible participants with whom the provider has not yet discussed SE or study participation to receive a “recruitment opt-in letter” describing study participation and requesting that Veterans contact their treating providers and/or the study team to learn more about the study. Study referrals will follow guidelines outlined above and below should the Veteran reach out to their provider and/or the research team to learn more about participation.

6. Provide the titles of the exact individuals who will have access to the collected data. **The following members will have access to the data: The PI, the Research Coordinator, the Independent Assessors, the Supported Employment Specialists, the Co-investigator, the Counseling Psychotherapist Supervisor, the Supported Employment Consultant, the co-investigator, the study biostatistician and the DMU administrators. Our study consultant, [name], will not have access to any study data. [name] will assist in the interpretation of the results of analyzed data.**
 - 6.1. Explain why these individual will have access to this data. **This is because these are the study staff that will be involved in collecting and entering the PHI into the database, or supervising the collection of PHI.**

Y. Information Security (Contact the Information Security Officer for additional assistance regarding confidentiality (storage/security) of research data.)

1. Provide the precise plan how data is to be collected or acquired (repeat the same information as listed under “Data Collection” section of this form. **At the baseline assessment interview, a member of the research team (PI, Co-I, or research coordinator) will administer a comprehensive, face-to-face interview that allows for a reliable diagnosis of schizophrenia and queries subject psychosocial functioning levels, symptomatology, substance use, service usage, and check-in. At other assessments, the independent assessor will perform semi-structured interviews, collect questionnaire data, administer cognitive and performance tests, and complete the check-in. The Supported Employment Specialists will complete the check-ins after treatment groups begin, which are not tied to an assessment (i.e., at 3-months, 9-months, and 15-months). They will collect data from the WBI at baseline, and at 6-months, 12-months, and 18-months after treatment groups begin (obtained in the course of standard SE care).**

Some data (e.g., demographics, diagnosis, study enrollment and tracking) will be stored on the centralized VA server and uploaded daily (i.e., \\VHAPHIFPCMIRECC \\Research Studies\\[name] -Integrated CBT to Improve Work). Research data from the questionnaires and some study scales (e.g., SAPS, BSES-SF) will be collected electronically via web interface, a password protected website run within the CMCVAMC firewall and stored on the VHAPHIFOCMIRECC direct-entry data server. The server is maintained by CMCVAMC FITS. Interview data and self-report data are entered directly onto computers at the research site, by research technicians and study subjects respectively. The technician will be present with the subject through the entire

assessment, and will review each instrument as it is completed. CNB data are uploaded automatically to the VA MIRECC secure server using PGP encryption and reviewed for validity (i.e., \\VHAPHIFPCMIRECC \\Research Studies\\[name] -Integrated CBT to Improve Work).

Data from the cognitive remediation program will also be stored on the Posit Science server for quality assurance/quality improvement analysis of the program by the Posit Science Company. All data sent to Posit Science will be coded and the code will not be available to them. The participants will be logged on to the Brain HQ server (by their SE specialist) using a coded number, separate from their study ID number. The Posit Science/Brain HQ Company will have no access to the study ID number at any time and will not be able to de-code the data in any way. No identifying information will be included with the data stored on the Posit Science server (https://portal.brainhq.com/?study=best_vet). Data will be saved on the VA server (i.e., \\VHAPHIFPCMIRECC \\Research Studies\\[name] -Integrated CBT to Improve Work).

Media recordings of the therapy sessions will be stored on the centralized VA server and uploaded daily (i.e., \\VHAPHIFPCMIRECC \\Research Studies\\[name] -Integrated CBT to Improve Work). Recordings will include the subjects' faces, bodies, and voices.

December 2015 amendment to change data storage location: Due to a system failure of the DMU at the VA, which was the main interface for entering research data for clinical studies for Behavioral health / MIRECC, an amendment to this ongoing protocol was made to change where data was stored (as detailed above and in below sections that describe data storage). This is being done with the input from the ISO and PO, and under the current PENN-VA MOU on data storage (even though there is a separate PENN component to our study). The need to use the DMU at Penn is critical because the use of pen/paper has many problems related to privacy and errors and storage.

Data from the 2 subjects enrolled, but not randomized, will not go to Penn. Data from the 2 subjects randomized, but not active, will not go to Penn. We will re-consent all active subjects (n=6); data for these subjects will only be entered in to the Penn DMU server after re-consent/agreement from participants.

We also note that there was no data loss due to the VA DMU failure.

April 2016 Amendment to change data storage location from Penn's Data Management Unit (DMU) back to VA DMU. NOTE: VA DMU server issues were fixed prior to finalization of UPenn DMU server for this study; no participant data was entered in the UPenn DMU server.

2. Provide a listing of the exact research data that will be stored, including but not limited to signed, original informed consent and HIPAA authorization forms, case report forms, etc. **Informed Consent Forms, HIPAA authorizations, tests, recorded sessions, and questionnaires/surveys.**
3. Indicate how project's research data (original and all copies) will be stored and provide corresponding security systems. **The participant's research records containing any personal health information will never leave the VA grounds.** Hard copies of consents, HIPAA authorizations, tests, and surveys, and recorded sessions, will be stored inside of a locked cabinet in the principal investigator's locked office at the VA in the MIRECC of the CMCVAMC. Some electronic data, including overall study tracking files, will be maintained on the CMCVAMC secure server (i.e., \\VHAPHIFPCMIRECC \\Research Studies\\[name] -Integrated CBT to Improve Work). The data will be coded and the code will be maintained separate from the rest of the data, locked in a cabinet in the MIRECC.

CNB data are uploaded automatically to the VA MIRECC secure server using PGP encryption and reviewed for validity (i.e., vhaphiwebcnp2.v04.med.va.gov/). Data from the cognitive remediation program will also be stored on the Posit Science server for quality assurance/quality improvement analysis of the program by the Posit Science Company. All data sent to Posit Science will be coded and the code will not be available to them. The Posit Science/Brain HQ Company will have no access to the study ID number at any time and will not be able to de-code the data in any way. No identifying information will be included with the data stored on the Posit Science server (https://portal.brainhq.com/?study=best_vet). Data will be saved on the VA server (i.e., \\VHAPHIFPCMIRECC \\Research Studies\\[name] -Integrated CBT to Improve Work). Research assessment data (including questionnaire data, clinical assessment data – including use of alcohol/substances, performance measures, supported employment tracking and fidelity ratings, and treatment group tracking data) will be housed on the VA DMU server ; data will be uploaded to the secure MIRECC server at least quarterly, for long-term storage (i.e., \\VHAPHIFPCMIRECC \\Research Studies\\[name] -Integrated CBT to Improve Work). NOTE: VA DMU server issues were fixed prior to finalization of UPenn DMU server for this study; no participant data was entered in the UPenn DMU server.

4. Provide exact location where research data (original and all copies) will be stored and secured. **Physical research data will be stored in the MIRECC, CMCVAMC. Some electronic data, including overall study tracking files, will be maintained on the CMCVAMC secure server. CNB data are uploaded automatically to the VA MIRECC secure server using PGP encryption and reviewed for validity (i.e., \\VHAPHIFPCMIRECC \\Research Studies\\[name] -Integrated CBT to Improve Work). The data will be coded and the code will be maintained separate from the rest of the data, locked in a cabinet in the MIRECC. Data from the cognitive remediation program will also be stored on the Posit Science server for quality assurance/quality improvement analysis of the program by the Posit Science Company. All data sent to Posit Science will be coded and the code will not be available to them. The Posit Science/Brain HQ Company will have no access to the study ID number at any time and will not be able to de-code the data in any way. No identifying information will be included with the data stored on the Posit Science server (https://portal.brainhq.com/?study=best_vet). Data will be saved on the VA server (i.e., \\VHAPHIFPCMIRECC \\Research Studies\\[name] -Integrated CBT to Improve Work). Research assessment data (including questionnaire data, clinical assessment data – including use of alcohol/substances, performance measures, supported employment tracking and fidelity ratings, and treatment group tracking data) will be housed on the VA DMU server; data will be uploaded to the secure MIRECC server at least quarterly, for long-term storage (i.e., \\VHAPHIFPCMIRECC \\Research Studies\\[name] -Integrated CBT to Improve Work).**
5. Explain how data is to be transported or transmitted from one location to another. **Data from the cognitive remediation program will be stored on the Posit Science server for quality assurance/quality improvement analysis of the program by the Posit Science Company. All data sent to Posit Science will be coded and the code will not be available to them. The Posit Science/Brain HQ Company will have no access to the study ID number at any time and will not be able to de-code the data in any way. No identifying information will be included with the data stored on the Posit Science server (https://portal.brainhq.com/?study=best_vet). Data will be saved on the VA server (i.e., \\VHAPHIFPCMIRECC \\Research Studies\\[name] -Integrated CBT to Improve Work). Research assessment data (including questionnaire data, clinical assessment data – including use of alcohol/substances, performance measures, supported employment tracking and fidelity ratings, and treatment group tracking data) will be housed on the VA DMU server; data will be uploaded to the secure MIRECC server at least quarterly, for**

long-term storage (i.e., \\VHAPHIFPCMIRECC \\Research Studies\\[name] -Integrated CBT to Improve Work).

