Eligible subjects who give a second informed consent will be randomly assigned to receive either iCBT or to usual care. All randomized participants will enter into supportive employment at the CMCVAMC. iCBT will be delivered as a group therapy for 12 months of weekly or biweekly sessions (see below). iCBT sessions will take approximately 1 hour. Blind, reliable independent assessors will reassess participants every 6 months after participants begin treatment groups over an 18-month participation period, producing mid-treatment (6 month) end-of-treatment (12 month), and post-treatment (18 month) assessments. Follow-up assessment procedures will take approximately 3-4 hours. The Research Coordinator will conduct a 15-minute Check-In at baseline to gather information about medications and services being received outside of this research study; the Supported Employment Specialists or Independent Assessors will conduct the 15-minute Check-In every 3 months after participants begin treatment groups (i.e., at 3-, 6-, 9-, 12-, 15-, and 18-months). The SE Specialists will also conduct the assessment of employment variables at these Check-Ins using the Workforce Participation form using an informal interview assisted by the use of a calendar and review of holidays and other activity anchors, supplemented by the ongoing assessment they conduct as part of the SE activities.

We are proposing a prospective randomized controlled trial with participants recruited from the CMCVAMC. We will randomize 96 patients (48 patients per condition). Independent assessors will be blinded to participant treatment group allocation. Assessment sessions will occur at baseline, and at 6, 12, and 18 months after therapy groups begin; brief check-ins will occur at each assessment session, and also at months 3, 9, and 15 after therapy groups begin.

Subjects in the iCBT condition will receive weekly or twice weekly group sessions for 12 months. iCBT follows a treatment manual developed by Perivoliotis, Grant, & Beck. The manual details the approach (engagement, behavioral activation, cognitive remediation/restructuring, maintenance) and individualized treatment planning. It also describes strategies and techniques to deal with positive and negative symptoms, mood symptoms, and suicidality. Included in these strategies are mindfulness exercises, designed to assist the participant in identifying feelings and biological processes that accompany a stimulus (i.e.,

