Beck Cognitive Insight Scale (BCIS).⁶⁷ The BCIS is a 15-item measure of two components (factors) of cognitive insight—the capacity and willingness to observe one’s experiences and consider alternative explanations (self-reflectiveness) and the overconfidence in the validity of one’s beliefs (self-certainty). Sample items include, “There is often more than one possible explanation for why people act the way they do” and “My interpretations of my experiences are definitely right.” In the original study with inpatients of varying diagnoses, the BCIS showed adequate convergent and discriminant validity and internal consistency ($\alpha = .60-.68$). The original psychometrics and factor structure have now been replicated several times.⁶⁹ Taken together, the research on the BCIS suggest that cognitive insight has important clinical significance for people with schizophrenia, that it may be a mediating variable in cognitive therapy for the disorder, and that it should therefore be assessed and addressed in clinical trials.⁶⁹

Collection of information from the Work Behavior Inventory (WBI).⁵⁵ The WBI is a 35-item scale specifically designed to assess the work behaviors of individuals suffering from severe mental illness. The WBI is completed as a routine standard of care measure during Supported Employment procedures. As part of usual care, the SE Specialists observes the patient in his/her work setting and also speak to the subject’s supervisor (when the veteran allows this). As part of the research study, we will collect information from the WBI at the time of the baseline and follow-up assessments. The measure will have a value of ‘0’ at points in which the participants are not working. WBI data may be missing if research participants refuse to allow the SE specialist to observe at the worksite and/or speak to employers. Data from the WBI will be analyzed along with other research data whenever available. The WBI is broken down into specific areas, including social skills, cooperativeness, work habits, work quality, and personal presentation. Each item is scored on a 5-point scale, with higher totals indicating stronger work performance. The WBI has been found to have good validity and reliability⁵⁵ and predicts vocational outcomes and productive activity after discharge from rehabilitation.

Performance measures

a) Cognitive

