2.1.1. Inclusion criteria

The study inclusion criteria are as follows:

- i. Diagnosis of DSM-IV schizophrenia or schizoaffective disorder (SCID)
- ii. Severe/extreme functional disability [World Health Organization Disability Assessment Scale (WHODAS) score ≥ 50]
- iii. Clinical stability (as per primary mental health provider)
- iv. Receiving treatment at the Veterans Administration
- v. Minimal engagement in psychiatric rehabilitation services (just psychiatrist and therapist/case management in the last 6 months)
- vi. Eligible and willing to be enrolled in Supported Employment program
- vii. Age 18 to 65
- viii. Proficient in English
- ix. Able to give informed consent

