This study is powered to detect a clinically significant difference between iCBT and the usual care conditions. Meta-analysis of medical and behavioral outcomes indicates that a medium effect-size between conditions will have a significant impact on quality of life. In a previous study we observed an average effect of about $d=0.55$ SD. To allow for a somewhat smaller effect in this proposed study, we design our study to have 80% power to detect clinically significant effect of $d=0.5$ SD. In the pilot data, we found a within-subject correlation structure consistent with a stationary autoregressive process with correlation parameter 0.4. We also assume a dropout rate of 20% for these power calculations. With these assumptions on effect size, covariance structure, and dropout rates, and with a two-sided alpha level of 0.05, the methods of Hedeker et al.⁸⁶ estimate that a sample size of 48 subjects per group will provide 80% power for the test of our primary hypothesis.

We believe that this is a conservative estimate, based on the larger effect size observed in our prior study, and the higher than expected dropout rate used in the calculation. In addition, our analyses will use the baseline measure of Psychosocial Functioning as a covariate, which should reduce the standard errors in our test, and therefore increase the smallest detectable effect size.

4.2. Define plans for data and statistical analysis, including key elements of the statistical plan, stopping rules and endpoints.

Planned Analyses

(i) Overview

Logistic, log-linear and linear random effects models (hierarchical regression models) will be implemented with random intercepts and slopes for longitudinal binary, count, and continuous outcomes, respectively. These models will contain separate main effects for change from baseline to each follow-up visit at 6, 12, and 18 months, main effect for the treatment, and interactions between the visit and treatment indicator variables. For each of the primary (workforce participation indices) and the secondary (Work Behavior Inventory, Specific Levels of Function) outcomes, separate intent-to-treat (ITT) tests and estimates (with 95% confidence intervals) of randomized group contrasts at 6, 12, and 18 months will be obtained from the estimates of the respective time-treatment interactions.

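### Baseline WBI will be 0 for almost everyone, and the planned mixed model, on its natural reading, then misstates the standard errors of the WBI contrasts

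*Combined protocol and SAP*

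**What the plan says.** **Source of the rating.** Section O.2.1.1 states: "The WBI is completed as a routine standard of care measure during Supported Employment procedures". The SE specialist observes the veteran at work and, if allowed, speaks to the supervisor. The score is set to 0 "at points in which the participants are not working". One reason for missing values is given: "WBI data may be missing if research participants refuse to allow the SE specialist to observe at the worksite and/or speak to employers".

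**Timing of collection.** Section Y.1 says of the SE specialists: "They will collect data from the WBI at baseline, and at 6-months, 12-months, and 18-months after treatment groups begin", and adds that the data arise from standard SE care. Table 1 (section O.1.3) marks WBI at baseline as well.

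**Who enters, and when SE starts.** Section R.2.1.1 requires "Minimal engagement in psychiatric rehabilitation services (just psychiatrist and therapist/case management in the last 6 months" and "Eligible and willing to be enrolled in Supported Employment program". Section O.1.1 places SE after randomization: "All randomized participants will enter into supportive employment at the CMCVAMC".

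**Model.** Section W.4.2(i) specifies random intercepts and slopes, with "separate main effects for change from baseline to each follow-up visit at 6, 12, and 18 months", a treatment main effect and visit-by-treatment interactions. The group contrasts come from the interactions. No residual structure is stated. Nor does the plan say whether baseline WBI is an outcome row, a subtracted value or a covariate.

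**Use.** Sections W.4.2(ii) and (iii) test WBI across 6 and 12 months (labelled Primary Aim 1 in one place and Secondary Aim 1 in the other) and again at 18 months (Secondary Aims 2 and 3). Section L lists WBI as secondary.

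**The concern.** The rating depends on SE contact that the entry rules place after the baseline visit. Together with the zero rule for non-workers, this makes baseline WBI close to a constant. A linear model with random intercept, random slope and one residual variance cannot represent a visit with no variance followed by three visits with full variance. It compromises by giving baseline too much variance and letting variance grow along the slope.

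Because each contrast is a change from baseline, that compromise feeds directly into its standard error. At stake are the width of the confidence intervals and the true error rate of the 6-, 12- and 18-month WBI comparisons.

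**Working it through.** **1. Is baseline WBI constant?** Non-workers score 0 by rule. Workers can be rated only through SE, which eligible patients have yet to enter. So baseline is 0 except for anyone already working, and someone working outside SE has no described route to a rating. The calculation below takes the limiting case of baseline variance 0.

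**2. The plan's own figure.** Inputs from section W.4.1: d = 0.5, autoregressive correlation 0.4, 20% dropout, two-sided alpha 0.05, 80% power. Take the mean of the 6- and 12-month visits, with retention 100% then 80% (an assumed split of the dropout):

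- Variance = 0.25 + 0.25/0.8 + 0.5 × 0.4 = 0.7625.
- n = 2 × (1.960 + 0.842)² × 0.7625 / 0.5² = 47.9, i.e. 48 per group, as stated.

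This version has no noisy baseline in the contrast.

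**3. What the model implies.** Score visits 0, 1, 2, 3. The true covariance is 0 at baseline, then variance 1 with correlation ρ^|i−j| at follow-up. Fit random intercept, random slope and common residual in large samples, by minimising log|V| + tr(V⁻¹C), where V is the model covariance and C the true one. At ρ = 0.4 the fitted baseline variance is 0.50 when the truth is 0.

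The intercept cancels from a change from baseline, so the model variance at visit t is t² × (slope variance) + 2 × (residual variance). For the mean of visits 1 and 2 it is 1.5² × (slope variance) + 1.5 × (residual variance). The true values are 1 and (1 + ρ)/2. The factor 2/n is common to both and cancels.

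At ρ = 0.4 the fitted slope variance is 0.052 and the residual variance 0.485:

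- 6 months: √(0.052 + 0.970) = 1.01
- 12 months: √(0.208 + 0.970) = 1.09
- 18 months: √(0.468 + 0.970) = 1.20
- Mean of 6 and 12 months: √[(0.117 + 0.728)/0.70] = 1.10

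Actual alpha is 2 × [1 − Φ(1.96 × ratio)]. Ratios, with actual alpha in brackets:

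| ρ | Slope var. | Residual var. | 6 m | 12 m | 18 m | Mean 6/12 m |
|---|---|---|---|---|---|---|
| 0.4 (protocol) | 0.052 | 0.485 | 1.01 (0.048) | 1.09 (0.033) | 1.20 (0.019) | 1.10 (0.031) |
| 0.6 (assumed) | 0.064 | 0.372 | 0.90 (0.078) | 1.00 (0.050) | 1.15 (0.024) | 0.94 (0.066) |
| 0.8 (assumed) | 0.075 | 0.244 | 0.75 (0.142) | 0.89 (0.082) | 1.08 (0.034) | 0.77 (0.131) |

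**4. Power at ρ = 0.4.** A contrast with 80% power under the correct standard error keeps Φ(2.802 − 1.96 × ratio):

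- 6/12-month mean: Φ(2.802 − 2.154) = 0.74.
- 18 months: Φ(2.802 − 2.352) = 0.67.

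With the step 2 inputs at 48 per arm, 0.5/√(2 × 0.7625/48) = 2.805. Power is then Φ(2.805 − 1.960) = 0.80 with the correct standard error and Φ(2.805 − 2.154) = 0.74 with the model's.

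**5. Checks.**

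- Simulation at 48 per arm, ρ = 0.4: ratios 1.03, 1.12 and 1.17 at 6, 12 and 18 months.
- Zeros at follow-up too (assumed 15–50% working, worker mean 125, SD 20): 1.07–1.30 at ρ = 0.4 and 0.90–1.14 at ρ = 0.8.
- Same model with an ordinarily varying baseline, ρ = 0.4: 0.96–1.03.
- Baseline row removed: 0.95–1.03. The zero baseline is therefore the source of the distortion.

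**The case against.** **The model feature is inferred.** The plan does not say that baseline is an outcome row or that residual variance is common. If baseline is subtracted or used as a covariate, a constant drops out and the error does not arise. Section W.4.1 does mention a baseline covariate, though for psychosocial functioning. This objection stands as a condition on the result. Still, three visit effects defined against baseline, plus a treatment main effect and interactions, most naturally describe baseline as a row, and no visit-specific variance is provided for.

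**Baseline may not be exactly constant.** No criterion requires unemployment, the Compensated Work Therapy program is a recruitment source (section R.2.2), and section H mentions patients enrolled in SE but inactive. This stands. In refits with 5% working and rated at baseline (0.05 × 48, or 2 to 3 per arm), 18-month inflation fell from 14–17% to 6–9%, under assumed working proportions and job persistence.

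**Stronger inferences that the documents do not support.**

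- A reader might infer that baseline WBI cannot be obtained. Non-workers have a defined value of 0, so the gap concerns only those already working outside SE.
- A reader might infer that the error is always conservative. It reverses at 6 months for the higher correlations in the table.
- A reader might infer a biased treatment effect. With both arms starting at 0, the contrast is unbiased.
- A reader might extend the result to the composite primary outcome or other workforce indices. Nothing was computed for them.

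**Conclusion.** The point holds conditionally. The documents make baseline WBI 0 for almost everyone and give no rating route for work outside SE at entry. On the natural reading of section W.4.2(i), the WBI standard errors are then wrong. At the protocol's own correlation they are too large, by about 10% for the 6/12-month mean and 20% at 18 months. At assumed correlations of 0.6 to 0.8 the 6-month standard error is 10–25% too small, while the 18-month one stays 8–15% too large.

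These figures rest on baseline being an outcome row, a common residual variance, and baseline variance of exactly zero. A few rated workers at baseline would shrink the 18-month effect. The issue concerns precision and error rates for WBI only. It should be fixed, because the plan leaves open a choice on which the validity of these tests depends.

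**What to change.** State in section W.4.2 that WBI is modelled at 6, 12 and 18 months only, with visit, treatment and visit-by-treatment terms and an unstructured covariance, and that the arm difference at each visit is the contrast. Alternatively, keep the baseline row and specify visit-specific variances or robust standard errors. If baseline turns out exactly constant, its variance would be estimated at the boundary of zero, so dropping the row is the more stable choice.

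Keep collecting baseline work status and WBI, both for description and for the baseline comparison that section W.4.2(i) uses to choose covariates. In section O.2.1.1, state how work outside SE at entry is scored.

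The cost is wording, with no new data. The downside is a few more covariance parameters and the loss of whatever little information a non-zero baseline carries.
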